3.1. Study Design Rationale

A placebo control will be used to establish the frequency and magnitude of changes in clinical endpoints that may occur in the absence of active treatment.

Randomization will be used to minimize bias in the assignment of patients to treatment groups, to increase the likelihood that known and unknown patient attributes (e.g., demographic and Baseline characteristics) are evenly balanced across treatment groups, and to enhance the validity of statistical comparisons across treatment groups.

Blinded treatment will be used to reduce potential bias during data collection and evaluation of clinical endpoints.

Study Population

The study population will consist of adult men and women with a diagnosis of moderate or severe MDD [i.e., met DSM-5 criteria for diagnosis of moderate or severe major depression with anxious distress and without psychotic features at Screening based on clinical assessment and on the SCID-5 (DSM-5 codes: 296.32, 296.33; ICD-10 codes: F33.1, F33.2)]. Patients should have at least one previous episode of depression prior to the one qualifying them for this study.

To minimize rating inflation, patients will qualify for the study by their own self ratings of their severity of depression by using the IDS-SR₃₀. Additional safeguards such as utilizing the Massachusetts General Hospital Clinical Trials Network Institute to conduct the “SAFER” interviews will be utilized (see Inclusion Criterion # 5). The SAFER inventory helps to facilitate identification of the *valid* patient for clinical trials. The inventory addresses specific elements adapted from the SAFER criteria that comprise a valid symptom and one SAFER element (face validity) that considers the entire symptom cluster as a valid nosological entity. Such criteria seek to confirm that identified patients have acute symptoms that reflect the current state of illness and that these symptoms can be reliably assessed with validated measurement tools. Beyond mere presence or absence, valid patients must have relevant symptoms that are pervasive, persistent (and not fluctuating over a defined period of time), and pathological in nature (Targum 2008).

Length of Study Phases and Periods

In any clinical study there is always some risk to removing current psychotropic medications and starting an investigational compound. All patients will undergo a Screening period including a washout period and a drug-free period of at least 7 days prior to randomization. Most patients will tolerate this washout period well without significant symptoms and can remain as outpatients with appropriate clinical monitoring and rescue medications. Only patients who have not had sufficient clinical benefit from their current psychotropic medication will be included in the study. Patients who are benefitting from their current psychotropic medications at the time of Screening will not be included in the study.

Tapering and discontinuation of the previous psychotropic medications will allow for the study drug to be assessed for efficacy and safety as monotherapy instead of an add-on therapy.

The 6-week duration of the double-blind study is adequate to assess the potential efficacy of MIN-117 in the treatment of MDD.

Dosage Selection and Interval

Clinical studies with MIN-117 have been shown the drug to be well tolerated at up to 7.5 mg/day for up to 14 days, and at up to 2.5 mg for 6 weeks. The selected doses (5.0 mg and 2.5 mg) are considered to be pharmacologically potent to show antidepressant effect as doses as low as 0.001 and 1.0 mg/kg were found to be effective in the CMS model of depression in mice. A once daily dosing interval is customary in depression trials and the PK properties of MIN-117 support such dosing interval without undue accumulation.

Choice of Efficacy Measurements

Mood and Anxiety

The MADRS was designed for use in subjects with MDD to measure the overall severity of depressive symptoms. The scale has been validated, is reliable and is acceptable to regulatory health authorities as a primary scale to determine efficacy in major depression.

The CGI will provide an overall clinician-determined summary measure that takes into account all available information, including knowledge of the subject's history, psychosocial circumstances, symptoms, behavior, and the impact of the symptoms on the subject's ability to function. The CGI comprises two companion one-item measures evaluating the following: severity of psychopathology (CGI-S) from 1 to 7 and change from the initiation of treatment on a similar seven-point scale (CGI-I).

Hamilton Anxiety Scale (HAM-A) measures the severity of a subject's anxiety, based on 14 parameters, including anxious mood, tension, fears, insomnia, somatic complaints and behavior at the interview. The subject is asked to rate the gravity of each item using a 5-level scale – from 0 to 4, with 4 being the most severe – and afterwards, the results are collated and tabulated to determine the severity of anxiety.

Stress and Anhedonia

MIN-117 pharmacological profile and hypothesized mechanism of action suggest it will have beneficial effect on the perceived levels of stress and hedonic capacity. To that end, the PSS and SHAPS scales will be used in an exploratory fashion to help validate such potential benefit.

Sleep

Sleep dysfunction, manifesting as too much or too little sleep, can be an indicator of depression. In addition, sleep dysfunction can be a side effect of antidepressant medications. Sleep-related adverse effects range from somnolence to insomnia, and from interrupted sleep to lack of restful, refreshing sleep. The consequences of sleep dysfunction may extend to daytime functioning and health-related quality of life. (Devine 2005).

To date, numerous studies have explored the effects of antidepressants on sleep but less research has focused on the use of sleep-electroencephalogram (EEG) parameters as biomarkers for the therapeutic effects of antidepressant medication. In a prospective case-

control study with a relatively large sample size, abnormal sleep-EEG profiles were associated with poor cognitive behavioral therapy response (Thase 1996). Two commonly reported biomarkers for therapeutic response are (i) a pretreatment elevated rapid eye movement (REM) disinhibition and (ii) an initial tonic REM suppression measured at beginning of treatment. Furthermore, recorded sleep EEGs at Day 7 and at Day 42 of treatment with paroxetine and tianeptine show that REM density served as a predictor of paroxetine treatment response: changes in REM density showed an inverse correlation with changes in HAM-D scores (Murk 2003). In summary, most studies point toward REM disinhibition before treatment and REM suppression at treatment initiation as predictors for better antidepressant treatment outcome.

Sexual Functioning

Another common side effect of certain antidepressant medications is sexual dysfunction; sexual dysfunction can also be a symptom of depression. Sexual dysfunction can occur in any one or more phases of the sexual cycle, including desire, arousal, orgasm and resolution (Derogatis 2008). The Arizona Sexual Experiences Scale (A-SEX) addresses the areas of sexual functioning most commonly impaired by psychotropic drugs while being brief, easy to understand and less intrusive than other sexual functioning measures. It will be used in this study to explore the effect of MIN-117 on sexual dysfunction.

Neurotrophic/Inflammatory Markers

Several studies have suggested that major depression is associated with reduced neurotrophic and elevated inflammatory markers. Depressed subjects who respond to antidepressant treatment show quantitative reversal in these markers. Exploratory assessment of these factors is included as potential biomarkers to predict response, subject to confirmation in larger studies.

Cognition

Cognitive impairments are now widely acknowledged as an important aspect of MDD, and the DSM-5 lists impairment in cognition (i.e., diminished ability to think or concentrate or indecisiveness) as a criterion item in the diagnosis of a major depressive episode. Although executive function and memory seem to be particularly impaired in patients with MDD, other domains can be affected including processing speed (Keefe 2014). In the present study, DSST (processing speed) will be performed.

4. STUDY POPULATION

4.1. Inclusion Criteria

Patients must meet all of the following inclusion criteria to be eligible for participation in this study:

1. Patients must be able to read and understand the consent forms, complete study-related procedures, and communicate with the study staff.
2. Patients must have provided written consent to participate in the study and understand that they are free to withdraw from the study at any time.
3. Patients must have signed the informed consent form for pharmacogenomic research indicating willingness to participate in the pharmacogenomic component of the study

in order to participate in the optional pharmacogenomic component of this study. Refusal to consent for this component does not exclude a patient from participation in the clinical study.

4. Patients must be aged 18 to 65 years, inclusive, at Screening (Visit 1).
5. Meet DSM-5 criteria for diagnosis of moderate or severe^a major depression with anxious distress and without psychotic features at Screening based on clinical assessment and on the SCID-5 (DSM-5 codes: 296.32, 296.33; ICD-10 codes: F33.1, F33.2). Their major depressive episode must be deemed "valid" using the Massachusetts General Hospital (MGH) SAFER^b criteria interview administered by remote, independent raters.
6. Subjects must be within a body mass index (BMI) of ≥ 18 to < 35 kg/m² [BMI = weight (kg)/height (m)²] at Screening (Visit 1).
7. Subjects have a history of at least one previous episode of depression prior to the current episode.
8. Patient must have been treated with an antidepressant administered at an adequate dose and duration in the past for the treatment of Major Depression. An adequate treatment is defined as an antidepressant treatment for at least 4 weeks at at least the minimum therapeutic dose, for any particular antidepressant.
9. Current major depressive episode of at least 4 weeks in duration.
10. At Screening (Visit 1) and Baseline (Visit 2), patients must have a score ≥ 40 on the patient rated IDS-SR₃₀.
11. At Screening (Visit 1) and Baseline (Visit 2), patients must have a score ≥ 18 on HAM-A.
12. At Screening (Visit 1) and Baseline (Visit 2), patients must have a score ≥ 4 on the investigator-rated CGI-S.
13. Patients must be outpatients at the time of randomization (Baseline [Day 1]).
14. Patients must be in good general health prior to study participation with no clinically relevant abnormalities as assessed by the investigator and determined by: medical history, physical examination, vital signs, blood chemistry, hematology, urinalysis, and electrocardiogram (ECG).
15. If female, the patient must:
 - a. be post-menopausal, or
 - b. have had a hysterectomy or tubal ligation or be otherwise incapable of pregnancy, or

^a Several symptoms in excess of those required to make the diagnosis of MDD AND symptoms markedly interfere with occupational functioning or with usual social activities or relationships with others.

^b The acronym SAFER stands for interview's attention to the following criteria: State versus trait; Assessability; Face validity; Ecological validity; and Rule of three Ps [pervasive, persistent, and pathological].

-
- c. must agree to consistent use of 2 methods of contraception for the duration of the study and until 90 days after the last dose of study medication. One of which must be a highly effective method defined as one that results in a low failure rate (i.e. less than 1% per year) when used consistently and correctly. The following highly effective contraception methods acceptable for this study are hormonal contraception (oral or parenteral hormonal contraceptive) or placement of an intrauterine device. The following methods can be used as a second form of contraception during the study: Barrier methods for female patients include their partner's use of a condom or the subject's use of an occlusive cap (diaphragm or cervical/ vault caps) with spermicidal foam, gel, film, cream or suppository.
16. If male with partner of childbearing potential, must be willing to use one barrier method of contraception with his partner throughout the study (a condom or his partner's use of an occlusive cap [diaphragm or cervical/ vault caps]). His partner must also be using a highly effective method of birth control defined as one that results in a low failure rate (i.e. less than 1% per year) when used consistently and correctly such as sterilization, implants, injectables, combined oral contraceptives, and intrauterine devices for up to 90 days after the last dose of study treatment. The patient must agree to inform the investigator if his partner becomes pregnant during the course of the study.
17. Male patients who have been sterilized or have partners of non-childbearing potential (including homosexual men) are required to use one barrier method of contraception. This is to prevent unintended exposure of the partner to the study drug via seminal fluid (for male subjects, this must be a condom or their partner's use of an occlusive cap [diaphragm or cervical/vault caps]).
18. Female patients of childbearing potential must have a negative serum pregnancy test at Screening (Visit 1) and negative serum and urine pregnancy test at Baseline (Visit 2).

4.2. Exclusion Criteria

Potential patients who meet any of the following criteria will be excluded from participating in the study:

1. A DSM-5 diagnosis of current (active): panic disorder, obsessive compulsive disorder (OCD), post-traumatic stress disorder (PTSD), anorexia nervosa, or bulimia nervosa.
2. History or current diagnosis of a psychotic disorder, bipolar disorder, mental retardation, or borderline personality disorders, mood disorder with postpartum onset, somatoform disorders, fibromyalgia, or idiopathic medical conditions.
3. At significant clinical risk for suicidal or violent behavior.
4. History of treatment within last 6 months with electroconvulsive therapy (ECT), Vagus Nerve Stimulation (VNS), Deep Brain Stimulation (DBS), or Transcranial Magnetic Stimulation (TMS).
5. Potential patient who in the opinion of the investigator should not discontinue, or participate in washout of a prohibited concomitant medication.
6. Potential patient who demonstrate a greater than 25% decrease in depressive symptoms as reflected by the IDS-SR₃₀ total score from Screening visit to Baseline visit.

-
7. Active cardiovascular disease (including but not limited to: atrial fibrillation or flutter, second and third-degree atrioventricular heart block, resting supraventricular tachycardia >100 beats per minute, unstable ischemic heart disease, valvular abnormality, sick sinus syndrome or other condition requiring pacemaker) or diastolic blood pressure > 105 mmHg.
 8. Any serious, untreated, or unstable illnesses, such as: liver or renal insufficiency.
 9. Any significant pulmonary, endocrine, or metabolic disturbances.
 10. Documented disease of the central nervous system that could interfere with the study assessments (including but not limited to: stroke, tumor, multiple sclerosis, Parkinson's disease, Alzheimer's disease, Huntington's disease, seizure disorder requiring current anti-convulsants, traumatic brain injury or trauma, and neurosyphilis).
 11. Hypothyroidism or hyperthyroidism, unless stabilized by appropriate medication for at least 3 months prior to Screening (a normal thyroid-stimulating hormone [TSH] is required prior to randomization at Baseline).
 12. Any medical condition that can potentially alter oral enteral absorption (e.g., gastrectomy), metabolism (e.g., liver failure), or excretion (e.g., renal failure) of the study drug.
 13. History of alcohol or substance use disorders (except nicotine and caffeine) meeting DSM-5 criteria within 1-year prior to Screening visit.
 14. Positive alcohol and urine drug screen for opiates, cocaine, barbiturates, tetrahydrocannabinol, methadone, tricyclic antidepressants, benzodiazepines, and amphetamine/methamphetamine at Screening or Baseline. Patients with positive testing at Screening due to prescribed benzodiazepines, tricyclic antidepressants, barbiturates or opiates are accepted but must test negative at Baseline (Visit 2).
 15. Male patients who have pregnant partners.
 16. Female patients who are breast-feeding.
 17. Received an experimental drug or used an experimental medical device within 60 days before the planned start of treatment (Day 1) or have participated in 2 or more clinical trials in the previous 2 years.
 18. QTcF interval at Screening or Baseline greater than 450 msec for males and 470 msec for females.
 19. Patients requiring treatment with drugs likely to prolong QT.
 20. Patients with known hypersensitivity to MIN-117 or placebo or their excipients (refer to section 13.1 p. 64 of the protocol).
 21. Positive hepatitis B surface antigen, or hepatitis C antibody or Human Immunodeficiency Virus (HIV) 1 and 2 antibodies at Screening.
 22. Employees of the investigator or study center, when the employee has direct involvement in the proposed study or other studies under the direction of that investigator or study center; also family members of the employee or the investigator.

4.3. Prior and Concomitant Therapy

4.3.1. Prior Therapy

Any medication (including, but not limited to, over-the-counter medicines such as aspirin, antacids, vitamins, mineral supplements, and herbal preparations) that the patient is receiving at the time of Screening, or receives during the study, must be recorded on the appropriate eCRF along with the reason for use, dates of administration, and dosages.

- Women must remain on a highly effective method of birth control (see [Section 4.1, Inclusion Criteria](#)).
- Patients must not use antidepressant within 1 week of the time they will take their first dose of study medication, or MAO inhibitor medications within 2 weeks, or fluoxetine (Prozac) within 4 weeks of the time they will take their first dose of study medication (i.e., 5 half-lives of the antidepressant).
- Patients must not use other prescription medication within 7 days (or per study physician's recommendation) prior to Baseline (Day 1) visit except those allowed in [Attachment 1](#) (Allowed and Prohibited Concomitant Medications). An exception is that women using hormone replacement therapy or hormonal contraception who have been using it continuously for at least 30 days before dosing may take the medication.

Other exceptions justified by the patient's medical condition could be allowed after the Sponsor's Responsible Medical Officer approval (refer to [Section 4.3.2](#)).

- Patients must not use herbal medications (e.g., St. John's Wort, ephedra, ginkgo, ginseng, and kava kava) within 7 days prior to Baseline visit or during the study.

Information on the dose, date of last administration, length of time on medication and reason for stopping or changing the medication will be collected in the source documents and appropriate eCRF pages.

4.3.2. Concomitant Therapy

All medications except study drug, administered to a patient during the study, should be documented in the eCRF as concomitant medications.

In general, concomitant medications with primary CNS activity, as well as CYP 2C8 and CYP 3A4/5 inhibitors, CYP 2C8 and CYP 3A4/5 inducers, and concomitant medications metabolized through CYP 2C9 are not allowed in this study (refer to [Attachment 1](#)).

As the list of prohibited/allowed concomitant medications ([Attachment 1](#)) is not exhaustive, other concomitant medications justified by the patient's medical condition could be allowed on a case by case basis after Sponsor's Responsible Medical Officer approval.

As a general rule:

- Patients must not use psychotropic drugs other than the study medications at any time during the study. For a complete list of prohibited therapies, please refer to [Attachment 1](#).

-
- Patients must be strongly discouraged from using alcohol or illicit substances during the entire study.
 - Ongoing psychological treatment (eg, Cognitive Behavior Therapy, Interpersonal Psychotherapy, Psychodynamic Psychotherapy, etc.) if it started > 3 months prior to the double-blind treatment phase, if the investigator deems the psychological treatment to continue during the study.

Patients should be discontinued from the study if any prohibited medications are used during the study (the Sponsor's Responsible Medical Officer can allow exceptions).

4.3.3. Contraception

Patients who are sexually active must use, with their partner, 2 approved methods of highly effective contraception from the time of study drug administration until 90 days after the last dose of study drug.

Two or more of the following methods are acceptable and must include at least 1 barrier method:

- Surgical sterilization (i.e., bilateral tubal ligation/salpingectomy, hysterectomy for female patients or partners; vasectomy for male patients or partners).
- Placement of an intrauterine device or intrauterine system.
- Hormonal contraception (implantable, patch, oral, injectable).
- Barrier methods (for male patients, this must be a condom or their partner's use of an occlusive cap [diaphragm or cervical/vault caps]; for female patients, either their partner's use of a condom or the patient's use of an occlusive cap [diaphragm or cervical/vault caps] with spermicidal foam/gel/film/cream/suppository).

Male patients who have been sterilized or have partners of non-childbearing potential (including homosexual men) are required to use one barrier method of contraception (condom). This is to prevent unintended exposure of the partner to the study drug via seminal fluid.

Female patients who are not of childbearing potential, i.e., women who are post-menopausal (defined as spontaneous amenorrhea for at least 1 year or spontaneous amenorrhea for at least 6 months confirmed by an follicle stimulating hormone [FSH] result of ≥ 40 IU/mL) or permanently sterilized (e.g., tubal occlusion, hysterectomy, bilateral salpingectomy), are not required to use any contraception during this study.

Alternatively, true abstinence is acceptable when it is in line with the patient's preferred and usual lifestyle. If a patient is usually not sexually active but becomes active, they, with their partner, must comply with the contraceptive requirements detailed above.

4.3.4. Exposure to Partners During the Study

As there is a significant risk of drug exposure through the ejaculate (which also applies to vasectomized males) that might be harmful to the sexual partners, including pregnant partners, of male patients, barrier contraception should be used throughout the study and for 90 days after the last day of study drug administration.

4.3.5. Sperm Donation

Male patients should not donate sperm for the duration of the study and for at least 90 days after the last day of study drug administration.

4.3.6. Pregnancy

Patients will be instructed that if they/their partner become pregnant during the study, the pregnancy should be reported to the investigator. The investigator should also be notified of pregnancy occurring during the study but confirmed after completion of the study. In the event that a patient/patient's partner is subsequently found to be pregnant after the patient is included in the study, then consent will be sought from the partner and, if granted, any pregnancy will be followed and the status of mother and/or child will be reported to the sponsor after delivery. Any patient reporting a pregnancy during the study will be withdrawn from the study.

Men who plan to father a child or to donate sperm within 90 days after last study drug administration (Day 43 or early withdrawal) are not allowed to participate in the study.

Woman who are currently pregnant or nursing, or are planning to conceive a child within 90 days after the last study drug administration (Day 43 or early withdrawal) are not allowed to participate in the study.

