1.4.1. Pharmacokinetics

Healthy Subjects

After a single oral dose, MIN-117 was rapidly absorbed, with time to maximum drug concentration (T_{max}) occurring approximately between 2.5 and 4.5 hours post-dose. The $t_{1/2}$ of MIN-117 in plasma was between 43 and 52 hours post-dose. Dose-proportionality between 2.5 and 15 mg single oral doses was demonstrated.

Urine concentrations of MIN-117 were also evaluated. Urinary excretion of MIN-117 were very low and burdened with high inter-individual variability. Primary mechanism of elimination for MIN-117 appear to be non-renal clearance.

After multiple oral doses, MIN-117 was rapidly absorbed with a T_{max} varying from 3 to 4 hours. Steady state was estimated to be reached after 10 days of MIN-117 administration. Pharmacokinetic parameters (concentrations and AUCs) increased with MIN-117 dose on Day 1 and Day 14. Median T_{max} was in the same range for each MIN-117 dose on Day 1 and Day 14. Systemic clearance and apparent volume of distribution (Vd/F) were in the same range for each MIN-117 dose. Moderate value of Vd/F suggested that MIN-117 is distributed in water and some tissues. Fluctuation index and accumulation rate were in the same range for each MIN-117 dose.

The accumulation ratio was around 4 multiples for the drug with a terminal half-life of 50-60 hours with a $t_{1/2}$ of 82 to 105 hours.

For each MIN-117 dose studied (1 mg, 3 mg, 7.5 mg), after single dose or last dose, PK parameters increased with MIN-117 exposure, for MIN-117.

The effect of co-administration with food is not known as yet.

Patients with MDD

Blood samples were collected during the study pre-dose and approximately 3 to 4 hours post-dose (approximate time of maximum plasma concentration for MIN-117). The respective mean plasma levels of MIN-117 in the treatment groups were:

- MIN-117: mean post-dose levels of ≥ 4 ng/mL for the MIN-117 0.5 mg group and post-dose levels of ≥ 18 ng/mL for the MIN-117 2.5 mg group.

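### Reproductive precautions run to 90 days after the last dose, but the protocol text asks patients to report only pregnancies that occur during the study: a minor mismatch, cheap to align at the next amendment

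*Protocol*

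**What the plan says.** **Precautions.** Inclusion criterion 15c requires contraception in women "for the duration of the study and until 90 days after the last dose of study medication". Section 4.3.3 sets it for sexually active patients "from the time of study drug administration until 90 days after the last dose of study drug". For men, section 4.3.4 says "barrier contraception should be used throughout the study and for 90 days after the last day of study drug administration", and section 4.3.5 rules out sperm donation "for the duration of the study and for at least 90 days after the last day of study drug administration". Section 4.3.6 bars anyone planning to conceive, father a child or donate sperm within 90 days of the last dose, which it places at Day 43 or early withdrawal.

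**Request to patients.** Section 4.3.6 has patients told that "if they/their partner become pregnant during the study, the pregnancy should be reported to the investigator". It adds that the investigator should hear of a pregnancy confirmed after the study, provided it occurred during the study. Inclusion criterion 16, in section 4.1 and again in the synopsis, reads "The patient must agree to inform the investigator if his partner becomes pregnant during the course of the study".

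**Handling once a pregnancy is known.** Section 11.3.3 requires staff to report every pregnancy, including those in partners, within 24 hours of learning of it, and to follow the outcome. It gives no end date. Section 4.3.6 provides for follow-up, with the partner's consent, of a pregnancy discovered after inclusion. Under section 11.3.1 the sponsor evaluates late information that an investigator passes on.

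**The concern.** The reporting period written for patients is shorter than the period in which the sponsor asks them to avoid pregnancy. The sentence on late notice does not close the difference: it deals with late confirmation of a pregnancy that occurred during the study, not with conception afterwards. The handling rules do not close it either, because each starts from the site's knowledge. The last scheduled contact and the last pregnancy test are at Visit 6. As far as the protocol goes, a pregnancy starting later in the 90 days comes to light only if a patient volunteers something they were not asked to report.

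What is at stake is follow-up of a few pregnancy outcomes. The sponsor chose the 90 days itself, and section 11.3.3 says the effect on sperm is unknown.

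**Working it through.** The documents state no figure for this gap, so there is none to reproduce. The check is day arithmetic.

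**Inputs.** Last dose Day 43 (section 4.3.6). Visit 6 on Day 57, with Visits 5 and 6 each within ±3 days (Time and Events Schedule). Precautions to 90 days after the last dose. MIN-117 patients: 81 + 81 = 162 (section 10.1).

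**Can the study be read to include the 90 days?** Criterion 15c and sections 4.3.4 and 4.3.5 name the 90 days in addition to the study, which argues against it. Section 4.3.3 does not separate the two. No per-patient end is stated where the request is made, so three readings are possible.

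**Days without a reporting request**
- *Study ends at Visit 6.* Precautions end on Day 43 + 90 = 133. Gap = 133 − 57 = 76 days; 76/90 = 84%. With the windows, Visit 5 falls on Days 40 to 46 and Visit 6 on Days 54 to 60, so Visit 6 is 8 to 20 days after the last dose. Gap = 90 − 20 = 70 to 90 − 8 = 82 days (78% to 91%).
- *Study ends at Week 6 (patient completion, section 9.1).* Gap = 133 − 43 = 90 days.
- *Study ends at the last patient's last visit (section 16.9.1).* Gap = max(0, 76 − d), where d is the number of days from the patient's own Visit 6 to that date. It is nil once d reaches 76, and the full 76 for the last patient.

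**Position of the gap relative to washout.** Section 1.4.1 says that after a single dose the half-life "of MIN-117 in plasma was between 43 and 52 hours post-dose"; after multiple doses it gives an accumulation ratio "around 4 multiples for the drug with a terminal half-life of 50-60 hours". Five half-lives:
- 5 × 43 h = 215 h = 9.0 days
- 5 × 60 h = 300 h = 12.5 days

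Nominal Visit 6 is 57 − 43 = 14 days after the last dose, so none of the 76 days precedes expected washout. With Visit 6 only 8 days after the last dose, at most 12.5 − 8 = 4.5 days do.

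**Expected pregnancies on MIN-117 in the gap.** This takes 1% per year, the protocol's ceiling for a highly effective method used consistently and correctly, and counts every patient as a couple at risk.
- 76 days: 162 × 0.01 × 76/365 = 0.34
- 70, 82 and 90 days: 0.31, 0.36 and 0.40
- 76 days with half of the patients at risk (assumption): 81 × 0.01 × 76/365 = 0.17

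These counts are illustrative. Treating all patients as at risk overstates them, since section 4.3.3 recognises post-menopausal, sterilised and abstinent patients. Lapses in contraception after the last visit would raise the rate above 1%.

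**The case against.** The strongest reply is that little is lost in practice, and most of it stands. Staff reporting has no cut-off, follow-up is already provided for, and patients carry a card with a 24-hour number. Section 1.3.3 reports no genotoxic potential and no overt teratogenic potential. That does not settle effects on sperm, but it lowers the residual concern. Precaution and reporting periods need not be identical.

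Three stronger readings are tempting, and the documents do not support them.
- *That patients are never asked for late reports.* The patient information and consent pages are not in the material available, and they may already ask. Only the protocol text can be judged.
- *That a drug-exposed period goes unmonitored.* Section 4.3.4 calls the risk of exposure through semen significant, but that concerns drug still present, and the nominal gap follows expected washout. Section 1.4.1 also prints a half-life of 82 to 105 hours. Five times 105 h is 21.9 days, which would put 21.9 − 14 = 7.9 days of the gap before washout. The visible sentence does not tie that range to MIN-117, to which it has just given 50 to 60 hours, so it cannot carry the argument.
- *That 76 days is a fixed figure.* It belongs to one of three readings.

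What survives is that the handling rules govern what a site does once it knows; they do not widen what patients are asked to report.

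**Conclusion.** The mismatch is real on the text, and it is minor. The protocol asks for precautions over 90 days and for reports over a shorter, undefined period. The gap is 76 days if the study ends at Visit 6 (70 to 82 with windows), 90 days if at Week 6, and 76 days down to none if at the last patient's last visit.

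The case for closing it rests on the sponsor's own choice of 90 days and the unknown effect on sperm. It does not rest on expected drug exposure, nor on the number of cases, which is below one even with every patient counted as at risk at 1% per year. There is no effect on efficacy or power. This is a wording improvement for the next amendment, not a reason to raise one.

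**What to change.** At the next amendment:
- In section 4.3.6 and both copies of inclusion criterion 16 (section 4.1 and synopsis), extend the reporting request to *during the study or within 90 days after the last dose of study drug*.
- Leave the sentence in 4.3.6 on withdrawing a patient who reports a pregnancy as it is.
- State in section 11.3.3 that the existing notification form and outcome follow-up apply to that period.
- Align the patient information if it does not already say this.

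No visit, test or scheduled contact is added. The wording changes in four places, but it alters an inclusion criterion and a patient duty. It therefore needs ethics committee approval before use and regulatory submission as applicable (sections 15.2.2, 16.1 and 16.2.1), which is why it should travel with other changes. There may be a few late reports to follow to outcome. Capture will still depend on patients coming forward.
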